12.3 Vital Signs

Blood pressures and heart rate baselines for predialysis are defined as the mean of values obtained from the last 6 weeks of screening including Day 1 prior to the first dose.

Descriptive statistics for vital signs (e.g., systolic and diastolic blood pressure, MAP, pulse rate, and respiratory rate) and their changes from baseline at each visit and at the end of study will be presented by treatment group.

Vital sign values are potentially clinically significant (PCS) if they meet both the observed value criteria and the change from baseline criteria listed in Table 8. The number and percentage of subjects with post-baseline PCS values will be tabulated by treatment group. The percentages are to be calculated relative to the number of subjects with baseline and at least one post-baseline assessment. The numerator is the total number of subjects with at least one post-baseline PCS vital sign value. Shift tables may be presented. A supportive listing of subjects with post-baseline PCS values will be provided including the subject ID, study center, baseline, and post-baseline values. A listing of all AEs for subjects with PCS vital signs will also be provided.

Table 8. Criteria for Potentially Clinically Significant Vital Signs

Vital Sign Parameter	Flag	Criteria*	
		Observed Value	Change from Baseline
Systolic Blood Pressure (mmHg)	High	≥ 170	Increase of ≥ 20
	Low	≤ 90	Decrease of ≥ 20

Diastolic Blood Pressure (mmHg)	High	≥ 100	Increase of ≥ 15
	Low	≤ 50	Decrease of ≥ 15
Pulse Rate (bpm)	High	≥ 120	Increase of ≥ 20
	Low	≤ 50	Decrease of ≥ 20
Weight (kg)	High	-	Increase of $\geq 10\%$
	Low	-	Decrease of $\geq 10\%$
*A post-baseline predialysis value is considered as a PCS value if it meets both criteria for observed value and change from predialysis baseline, respectively.			

Additional analyses include but are not limited to

- Subgroup analyses of subjects without any change in BP meds during Treatment Period
- Proportion of subjects meeting National Kidney Foundation BP target: within sBP 120-140 mmHg/dBP 70-90 mmHg at baseline, during treatment, and 4 weeks post treatment

12.4 Electrocardiogram (ECG)

Descriptive statistics for ECG parameters (e.g., Heart Rate, PR interval, QRS interval, QT interval, and QTc interval) at baseline and changes from baseline at each assessment time point will be presented by treatment group. QTc interval will be calculated using both Bazett ($QTcB = QT / (RR)^{1/2}$) and Fridericia ($QTcF = QT / (RR)^{1/3}$) corrections; and if RR is not available, it will be replaced with 60/HR in the correction formula.

A plot for each parameter of mean (+/- 95% CI) versus visit will be produced by treatment group (roxadustat vs. Epoetin).

ECG parameters values are potentially clinically significant (PCS) if they meet or exceed the upper limit values listed in Table 9. The number and percentage of subjects with post-baseline PCS values will be tabulated by treatment group. The percentages are to be calculated relative to the number of subjects with available non-PCS baseline and at least one post-baseline assessment. The numerator is the total number of subjects with at least one post-baseline PCS ECG value. Shift tables may be presented. A listing for all subjects with post-baseline PCS value will be provided including the subject ID, study center, baseline, and post-baseline PCS values.

In addition, a listing of all TEAEs for subjects with PCS ECG values and a listing of subjects with post-baseline significant ECG abnormalities as reported by the investigators will also be provided.

Table 9. Criteria for Potentially Clinically Significant ECG

ECG Parameter	Unit	Higher Limit
QRS interval	Msec	≥ 150
PR interval	Msec	≥ 250
QTc interval	Msec	> 500 ; Change from baseline > 60

12.5 Other Safety Analyses

A separate meta-analysis SAP for pre-specified, adjudicated (blinded) composite safety endpoints to assess cardiovascular, cerebrovascular and thrombo-embolic events will be developed to complement this study specific SAP.

13 ADDITIONAL AND SUBGROUP ANALYSES

Selected efficacy and safety analyses may be performed separately by sex, age group, baseline iron replete status and baseline stratification factors.

14 INTERIM ANALYSES

Safety data and dosing decisions will be monitored on an ongoing basis. Additional ongoing review of safety data will be conducted by an independent data and safety monitoring board (DSMB).

Abbreviations: Ab = antibody; AE = adverse event; BP = blood pressure; CBC = complete blood count; cHR = reticulocyte hemoglobin content; cardiovascular = cardiovascular; ECG = electrocardiogram; ELISA = enzyme-linked immunosorbent assay; EOT = End of Treatment; ET=Early Termination; EOS = End of Study; HbA1c = glycated hemoglobin; HBsAg = hepatitis B surface antigen; hCG = human chorionic gonadotropin; Hcardiovascular = hepatitis C virus; HD = hemodialysis; HIV = human immunodeficiency virus; HR = heart rate; HRQoL = health-related quality of life questionnaire; hs-CRP = high-sensitivity C-reactive protein; ICF = informed consent form; LFTs = liver function tests; O = optional test/assessment; PE = physical examination; RBC = red blood cell; RR = respiratory rate; TIBC = total iron binding capacity; UIBC = unsaturated iron binding capacity; TSAT = transferrin saturation; WBC = white blood cells; Wk(s) = week(s); X = mandatory test/assessment.

Notes: In subjects on HD, all lab sampling is to be performed prior to the dialysis session.

Subjects who discontinue study medication prematurely will be followed up until the end of the study, unless consent to participate is withdrawn. Upon completion of EOT and EOS visits, these subjects will be followed up every 3-6 month interval for vital status, cardiovascular events, and hospitalization (depending on the availability of subjects) until study closure. These visits may occur either in-person or via telephone.

- a All screening procedures should be completed within 6 weeks. For subjects currently taking Mircera[®], the screening period can be extended up to 8 weeks.
- b Day 1 is a due treatment date per the existing ESA treatment schedule. All study assessments are to be performed prior to first study drug administration. In subjects on HD study assessments with the exception of HRQoL and body-weight measurement should also be performed prior to or at initiation of dialysis; HRQoL assessments should be done approximately during dialysis (preferably at the beginning) and weight measurement after dialysis.
- c Subjects discontinuing study medication prematurely will complete EOT and EOS. Unless consent is withdrawn, cardiovascular events, vital status and hospitalizations will be collected every 3 to 6 months (phone or in-person clinic visit) for these subjects until study closure
- d Targeted PE (general appearance, CV, respiratory and abdomen)
- e BP and HR should be measured using automated calibrated instruments at pre dialysis in subjects on HD and preferably approximately at the same time in subjects on PD. Measurement to occur prior to study drug administration (if applicable); BP and HR should be assessed per guidelines provided in Appendix 5
- f Respiratory rate should be measured at predialysis in subjects on HD and preferably approximately at the same time in subjects on PD. Measurement should occur prior to study drug administration (if applicable)
- g Separate hemoglobin samples should be collected at all the visits where a CBC is not collected (i.e., hemoglobin at Weeks 6, 10, 14, 16, 18, 22, 24, 32, 40, 48, etc)
- h Not required if result of a renal ultrasound report within 12 weeks prior to randomization is available
- i Collect from female subjects of childbearing potential only
- j Including SF-36, FACT-An, EQ-5D 5L, HRQoL assessments should be administered approximately at the same time of the day. Example: in HD subjects, questionnaires to be completed by subject approximately at the same time during dialysis and in PD subjects approximately at the same time of the day
- k Initial dosing of roxadustat and epoetin alfa per Tables 1 and 2, respectively. Dose adjustment per Appendix 2 (roxadustat subjects) or epoetin package insert or SmPC (epoetin subjects); dose review for predefined out of range hemoglobin elevations at every visit. All subjects on HD will receive epoetin alfa TIW intravenously (IV). For peritoneal dialysis subjects, the route of administration (IV or SC) of epoetin alfa may remain the same as baseline (per discretion of the Investigator)
- l Subjects randomized to roxadustat: dose adjustment begins at Week 4 refer to Appendix 2

Notes: In subjects on HD, all lab sampling is to be performed prior to the dialysis session.

16.2 Appendix 2 Roxadustat Dose Adjustment Rules

Following Day 1, at each study visit during the Treatment Period, hemoglobin will be measured (prior to dialysis in HD subjects) locally to determine the need for a dose adjustment or to assess for predefined out of range hemoglobin elevations. This local hemoglobin measurement may be made with the use of a point-of-care device (e.g., HemoCue[®], CritLine[®]) or by local laboratory (i.e., Stat Lab*) testing if the point-of-care device is not available or the result is considered unreliable. In the event that the hemoglobin value of the visit as determined by the study central laboratory is significantly different from that measured locally, and per Investigator that warrants a reversal of the dose adjustment decision made earlier based on locally measured hemoglobin value, the Medical Monitor should be informed, if possible.

In this study, a rate of rise of hemoglobin > 2 g/dL in 4 weeks or a hemoglobin level of ≥ 13 g/dl at any time would be considered as excessive haematopoiesis and would require either dose reduction or temporary dose hold.

The dose of roxadustat will remain constant during the first 4 weeks of the Treatment Period unless a dose reduction is required for predefined out of range hemoglobin elevations. Roxadustat dose adjustments are permitted from Week 4 onwards, and every 4 weeks thereafter (e.g., Week 4, Week 8, Week 12); however, the dose may be adjusted between two prespecified windows (e.g., anytime between Week 4 and Week 8 visits, Week 8 and Week 12 visits) if all of the following criteria are met:

- No dose adjustment has been made in last 4 weeks
- Hemoglobin < 9.0 g/dL.

Any dose adjustment will reset the dose-adjustment window to every 4 weeks thereafter (e.g., dose adjustment for a qualified reason at Week 6 leads to next dose adjustment at Week 10).

Dose adjustment must not be done sooner than 4 weeks unless discussed with and preapproved by the medical monitor. Dose adjustments for roxadustat are described in the Table 10 below.

Subjects randomized to roxadustat will take doses TIW for the entire duration of the Treatment Period. Dosing frequency may only be adjusted to BIW or QW if a subject requires < 20 mg TIW (i.e., < 60 mg per week) to maintain a hemoglobin level of approximately 11 g/dL. The Medical Monitor should be notified as soon as possible of such dose change.

Table 10. Roxadustat Dose Adjustment Rules

Change in hemoglobin over past 4 weeks (g/dL)	Hemoglobin (g/dL) at Dose Adjustment Review Visit			
	< 10.5	10.5 to < 12.0	12.0 to < 13.0	≥ 13.0
< -1.0	↑	↑	No change	Hold dosing, check hemoglobin at least weekly, then resume dosing when hemoglobin < 12.0 g/dL, at a dose that is reduced by one dose step
-1.0 to 1.0	↑	No change	↓	
> 1.0	No change	↓	↓	

Abbreviations: ↑ = increase; ↓ = decrease.

Notes:

Dose Increases and Reductions:

- Dose increases (↑) and reductions (↓) are preset.
- The dose steps are as follows: 20, 40, 50, 70, 100, 150, 200, 250, 300, and 400 mg. For example, a subject previously receiving 70 mg of roxadustat requiring a dose increase would have his dose changed to 100 mg of roxadustat. A subject previously receiving 150 mg of roxadustat requiring a dose reduction would have his dose changed to 100 mg of roxadustat. Medical Monitor should be informed when < 20 mg /dose is required.
- The maximum dose is capped at 400 mg or 3.0 mg/kg/dose (whichever is lower).

Dose Adjustment for predefined out of range hemoglobin elevations:

- If hemoglobin increases by > 2.0 g/dL at any time within 4 weeks, the dose should be reduced by one dose step.
- Only one dose reduction for predefined out of range hemoglobin elevations is recommended within a period of 4 weeks.
- Temporary dose holds for predefined out of range hemoglobin elevations should be confirmed based on central lab hemoglobin assessments. Upon confirmation, if the hemoglobin is ≥ 13 g/dL, withhold dosing, check hemoglobin at least weekly, then resume dosing when hemoglobin < 12.0 g/dL, at a dose that is reduced by one dose step. The subsequent hemoglobin follow-up assessments should also be done by a central lab.

* A "Stat lab" is to be used only for urgent lab test that is needed for immediate decision making related to protocol, management of adverse events as determined by the Investigator.

16.3 Appendix 3 SF-36 (Version 2)

Your Health and Well-Being

This survey asks for your views about your health. This information will help keep track of how you feel and how well you are able to do your usual activities. *Thank you for completing this survey!*

For each of the following questions, please tick the one box that best describes your answer.

1. In general, would you say your health is:

Excellent	Very good	Good	Fair	Poor
▼	▼	▼	▼	▼
 1	 2	 3	 4	 5

2. Compared to one year ago, how would you rate your health in general now?

Much better now than one year ago	Somewhat better now than one year ago	About the same as one year ago	Somewhat worse now than one year ago	Much worse now than one year ago
▼	▼	▼	▼	▼
 1	 2	 3	 4	 5

SF-36 (Version 2)

3. The following questions are about activities you might do during a typical day. Does your health now limit you in these activities? If so, how much?

Yes, limited a lot	Yes, limited a little	No, not limited at all
▼	▼	▼

- a Vigorous activities, such as running, lifting heavy objects, participating in strenuous sports ₁ ₂ ₃
- b Moderate activities, such as moving a table, pushing a vacuum cleaner, bowling, or playing golf ₁ ₂ ₃
- c Lifting or carrying groceries ₁ ₂ ₃
- d Climbing several flights of stairs ₁ ₂ ₃
- e Climbing one flight of stairs ₁ ₂ ₃
- f Bending, kneeling, or stooping ₁ ₂ ₃
- g Walking more than a mile ₁ ₂ ₃
- h Walking several hundred yards ₁ ₂ ₃
- i Walking one hundred yards ₁ ₂ ₃
- j Bathing or dressing yourself ₁ ₂ ₃

SF-36 (Version 2)

4. During the past 4 weeks, how much of the time have you had any of the following problems with your work or other regular daily activities as a result of your physical health?

All of the time	Most of the time	Some of the time	A little of the time	None of the time
▼	▼	▼	▼	▼

- a Cut down on the amount of time you spent on work or other activities ₁ ₂ ₃ ₄ ₅
- b Accomplished less than you would like ₁ ₂ ₃ ₄ ₅
- c Were limited in the kind of work or other activities ₁ ₂ ₃ ₄ ₅
- d Had difficulty performing the work or other activities (for example, it took extra effort) ₁ ₂ ₃ ₄ ₅

5. During the past 4 weeks, how much of the time have you had any of the following problems with your work or other regular daily activities as a result of any emotional problems (such as feeling depressed or anxious)?

All of the time	Most of the time	Some of the time	A little of the time	None of the time
▼	▼	▼	▼	▼

- a Cut down on the amount of time you spent on work or other activities ₁ ₂ ₃ ₄ ₅
- b Accomplished less than you would like ₁ ₂ ₃ ₄ ₅
- c Did work or other activities less carefully than usual ₁ ₂ ₃ ₄ ₅

SF-36 (Version 2)

6. During the past 4 weeks, to what extent has your physical health or emotional problems interfered with your normal social activities with family, friends, neighbours, or groups?

Not at all	Slightly	Moderately	Quite a bit	Extremely
▼	▼	▼	▼	▼
□ ₁	□ ₂	□ ₃	□ ₄	□ ₅

7. How much bodily pain have you had during the past 4 weeks?

None	Very mild	Mild	Moderate	Severe	Very severe
▼	▼	▼	▼	▼	▼
□ ₁	□ ₂	□ ₃	□ ₄	□ ₅	□ ₆

8. During the past 4 weeks, how much did pain interfere with your normal work (including both work outside the home and housework)?

Not at all	A little bit	Moderately	Quite a bit	Extremely
▼	▼	▼	▼	▼
□ ₁	□ ₂	□ ₃	□ ₄	□ ₅

SF-36 (Version 2)

9. These questions are about how you feel and how things have been with you during the past 4 weeks. For each question, please give the one answer that comes closest to the way you have been feeling. How much of the time during the past 4 weeks...

	All of the time	Most of the time	Some of the time	A little of the time	None of the time
	▼	▼	▼	▼	▼
a Did you feel full of life?	 ₁	 ₂	 ₃	 ₄	 ₅
b Have you been very nervous? ,,,	 ₁	 ₂	 ₃	 ₄	 ₅
c Have you felt so down in the dumps that nothing could cheer you up?	 ₁	 ₂	 ₃	 ₄	 ₅
d Have you felt calm and peaceful?	 ₁	 ₂	 ₃	 ₄	 ₅
e Did you have a lot of energy? ,,,	 ₁	 ₂	 ₃	 ₄	 ₅
f Have you felt downhearted and low?	 ₁	 ₂	 ₃	 ₄	 ₅
g Did you feel worn out?	 ₁	 ₂	 ₃	 ₄	 ₅
h Have you been happy?	 ₁	 ₂	 ₃	 ₄	 ₅
i Did you feel tired?	 ₁	 ₂	 ₃	 ₄	 ₅

10. During the past 4 weeks, how much of the time has your physical health or emotional problems interfered with your social activities (like visiting with friends, relatives, etc.)?

All of the time	Most of the time	Some of the time	A little of the time	None of the time
▼	▼	▼	▼	▼
 ₁	 ₂	 ₃	 ₄	 ₅

SF-36 (Version 2)

11. How TRUE or FALSE is each of the following statements for you?

	Definitely true	Mostly true	Don't know	Mostly false	Definitely false
a I seem to get ill more easily than other people	 1	 2	 3	 4	 5
b I am as healthy as anybody I know	 1	 2	 3	 4	 5
c I expect my health to get worse	 1	 2	 3	 4	 5
d My health is excellent	 1	 2	 3	 4	 5

Thank you for completing these questions!

16.4 Appendix 4 FACT-An (Version 4)

Below is a list of statements that other people with your illness have said are important. Please circle or mark one number per line to indicate your response as it applies to the past 7 days.

PHYSICAL WELL-BEING		Not at all	A little bit	Some-what	Quite a bit	Very much
GP1	I have a lack of energy	0	1	2	3	4
GP2	I have nausea	0	1	2	3	4
GP3	Because of my physical condition, I have trouble meeting the needs of my family	0	1	2	3	4
GP4	I have pain	0	1	2	3	4
GP5	I am bothered by side effects of treatment	0	1	2	3	4
GP6	I feel ill	0	1	2	3	4
GP7	I am forced to spend time in bed	0	1	2	3	4

SOCIAL/FAMILY WELL-BEING		Not at all	A little bit	Some-what	Quite a bit	Very much
GS1	I feel close to my friends	0	1	2	3	4
GS2	I get emotional support from my family	0	1	2	3	4
GS3	I get support from my friends	0	1	2	3	4
GS4	My family has accepted my illness	0	1	2	3	4
GS5	I am satisfied with family communication about my illness	0	1	2	3	4
GS6	I feel close to my partner (or the person who is my main support)	0	1	2	3	4
Q1	Regardless of your current level of sexual activity, please answer the following question. If you prefer not to answer it, please mark this box  and go to the next section.					
GS7	I am satisfied with my sex life	0	1	2	3	4

FACT-An (Version 4)

Please circle or mark one number per line to indicate your response as it applies to the past 7 days.

EMOTIONAL WELL-BEING		Not at all	A little bit	Some-what	Quite a bit	Very much
GE1	I feel sad	0	1	2	3	4
GE2	I am satisfied with how I am coping with my illness	0	1	2	3	4
GE3	I am losing hope in the fight against my illness	0	1	2	3	4
GE4	I feel nervous	0	1	2	3	4
GE5	I worry about dying	0	1	2	3	4
GE6	I worry that my condition will get worse	0	1	2	3	4

FUNCTIONAL WELL-BEING		Not at all	A little bit	Some-what	Quite a bit	Very much
GF1	I am able to work (include work at home)	0	1	2	3	4
GF2	My work (include work at home) is fulfilling	0	1	2	3	4
GF3	I am able to enjoy life	0	1	2	3	4
GF4	I have accepted my illness	0	1	2	3	4
GF5	I am sleeping well	0	1	2	3	4
GF6	I am enjoying the things I usually do for fun	0	1	2	3	4
GF7	I am content with the quality of my life right now	0	1	2	3	4

FACT-An (Version 4)

Please circle or mark one number per line to indicate your response as it applies to the past 7 days.

ADDITIONAL CONCERNS		Not at all	A little bit	Some- what	Quite a bit	Very much
HI7	I feel fatigued	0	1	2	3	4
HI12	I feel weak all over	0	1	2	3	4
An1	I feel listless ("washed out")	0	1	2	3	4
An2	I feel tired	0	1	2	3	4
An3	I have trouble starting things because I am tired	0	1	2	3	4
An4	I have trouble finishing things because I am tired ..	0	1	2	3	4
An5	I have energy	0	1	2	3	4
An6	I have trouble walking	0	1	2	3	4
An7	I am able to do my usual activities	0	1	2	3	4
An8	I need to sleep during the day	0	1	2	3	4
An9	I feel lightheaded (dizzy)	0	1	2	3	4
An10	I get headaches	0	1	2	3	4
B1	I have been short of breath	0	1	2	3	4
An11	I have pain in my chest	0	1	2	3	4
An12	I am too tired to eat	0	1	2	3	4
BL4	I am interested in sex	0	1	2	3	4
An13	I am motivated to do my usual activities	0	1	2	3	4
An14	I need help doing my usual activities	0	1	2	3	4
An15	I am frustrated by being too tired to do the things I want to do	0	1	2	3	4
An16	I have to limit my social activity because I am tired	0	1	2	3	4

16.5 Appendix 5 Data Handling Conventions

16.5.1 Visit Time Windows

The table below presents the visits assigned for efficacy and safety analyses corresponding to the range of treatment days (window) during which an actual visit may have occurred.

Table 11. Visit Time Windows

Derived Visit	Scheduled Visit Day ^a	Window
Baseline, Week 0	Day 1	Days ≤ 1
Week 1	Day 7*(Week #)+1	Days [Day 2, 10]
Week 2	Day 7*(Week #)+1	Days [Scheduled Day ± 3 Scheduled Day ± 6]
Weeks 4 prior to 24	Day 7*(Week #)+1	Days [Scheduled Day ± 7 , Scheduled Day ± 6]
Week 24	Day 7*(Week #)+1	Days [Scheduled Day ± 7 Scheduled Day ± 13]
\geq Week 28	Day 7*(Week #)+1	Days [Scheduled Day ± 14 , Scheduled Day ± 13]
ET	Earlier Termination, match to a closest scheduled visit in protocol if patient had not been off drug for more than 7 days.	
EoT	Last assessment between Day 2 and EOT visit day, match to a closest scheduled visit in protocol if patient had not been off drug for more than 7 days.	
EoS (FU-4Wk)	Final visit for the Study 15 – 31 days after the last dose (excluding long term follow-up for early termination).	

^a: Relative to the first study medication date. For example, Day 1 = the first dose date of study medication.

Table 12: Analysis Visit Windows for QoL

CRF Visit	Target Day ^a	Analysis Visit Windows Actual Assessment Day	Analysis Visit
Day 1	Day 1	Day 1	Baseline
Week 12	Day 7 * (Week #) + 1	Target day -14, Target Day + 27	Week 12
Week 28	Day 7 * (Week #) + 1	Target Day – 28, Target Day +83	Week 28
Week 52	Day 7 * (Week #) + 1	Target Day – 84, Target Day + 83	Week 52
EOT Visit		Last assessment between Day 2 and EOT visit day, remapped to the closest next scheduled visit for HRQoL collection.	Week 12, 28, 52 and > 1 year

^a: Relative to Day 1 (first dose date of study medication)

Table 13. Analysis Visit Windows for Lipid Panel

Derived Visit	Scheduled Visit Day ^a	Window
Baseline, Week 0	Day 1	Day 1
Week 4	Day 7*(Week #)+1	[Day 2, Day +42]
Week 8	Day 7*(Week #)+1	[Scheduled Day-14, Scheduled Day +13]
Weeks 12	Day 7*(Week #)+1	[Scheduled Day -14, Scheduled Day +27]
Week 20, 28	Day 7*(Week #)+1	[Scheduled Day -28, Scheduled Day +27]
Weeks 36	Day 7*(Week #)+1	[Scheduled Day -28, Scheduled Day +41]
Week 48 to xx	Day 7*(Week #)+1	[Scheduled Day -42, Scheduled Day +41]
Week xx	.	Last assessment between Day 2 and EOT visit day, match to a closest scheduled visit in protocol if patient had not been off drug for more than 7 days
FU-4Wk		Final visit in the Study 15 – 31 days after Last Dose.

^a: Relative to Day 1 (first dose date of study medication)

Visit Day is calculated by (visit date – first dose date of study medication + 1). If a subject has ≥ 2 actual visits within the same window, the last visit with non-missing value will be used for analysis.

Repeated or Unscheduled Assessments of Safety Parameters

If a subject has repeated assessments prior to the start of study medication, then the results from the final assessment made prior to the start of study medication will be used as baseline. If end of study assessments are repeated or unscheduled, the last post-baseline assessment will be used as the end of study assessment for generating summary statistics. However, all post-baseline assessments will be used for PCS value determination and all assessments will be presented in the data listings.

Missing Date of Study Medication

When the last date of study medication during the study treatment phase is missing, all efforts should be made to obtain the date from the investigator. If it is still missing after all efforts, then the last visit date during the Treatment Period will be used in the calculation of treatment duration.

Missing Severity Assessment for Adverse Events

If severity is missing for an AE started prior to the first study medication, then a severity of “Mild” will be assigned. If the severity is missing for an AE started on or after the first study medication dosing, then a severity of “Severe” will be assigned. The imputed values for severity assessment will be used for incidence summary, while the actual missing values will be presented in data listings.

Missing Relationship to Study Drug for Adverse Events

If the relationship to the study medication is missing for an AE started after baseline, a causality of “Related” will be assigned. The imputed values for relationship to study medication will be used for incidence summary, while the actual values will be presented in data listings.

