#### **7.1.2.3 Weeks 4 to 24 (Every 2 weeks, $\pm 4$ days)**

- Laboratory tests (must be performed prior to dosing):
  - Week 4, 8, 12, 20: CBC with WBC differential
  - Week 6 followed by every visit where no CBC is collected: Hb only
  - Week 4, 8, 12, 20: Serum chemistry
  - Weeks 6, 16, 24: LFTs only
  - Weeks 4, 8, 12, and 20: Lipid panel
  - Weeks 4, 8, 12, 20: Serum iron, ferritin, TIBC, UIBC, TSAT
  - Weeks 4, 6, 8, 12, 16, 20: Reticulocyte count and CHr
  - Weeks 12, 24: HbA1c
  - Weeks 4, 12, 20: Special laboratory analytes (hs-CRP, hepcidin)
  - Weeks 4, 12, 20: Archival serum and plasma samples
  - Weeks 12, 24: Serum hCG pregnancy test for women of childbearing potential only

- Weeks 12, 24: Targeted physical examination
- Dose adjustment review: At Week 4, followed by every 4 weeks.
- Weeks 24: 12-lead ECG
- Week 12: HRQoL questionnaires (SF-36, FACT-An, and EQ-5D-5L)\*

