5.4 Additional Data Handling Rules and Presentation Specifications

The following general guidelines will apply to all statistical analyses and data presentations:

- Baseline is defined as the last available value obtained prior to the first dose of study drug, unless otherwise specified in this SAP.
- Hemoglobin baseline is defined as the mean of the at least last three available central laboratory hemoglobin values obtained prior to the first dose of study medication (three

of the latest screening hemoglobin values plus the predose hemoglobin value collected on Day 1). In subjects with missing Day 1 hemoglobin value, the mean of three latest screening laboratory hemoglobin values will be considered as baseline hemoglobin value.

- Baselines for reticulocyte count, reticulocyte hemoglobin content (CHr), hepcidin, hs-CRP, serum iron parameters (transferrin, TIBC, ferritin, sTfR, and iron), blood pressures and heart rate are defined as the mean of central lab values obtained within 6 weeks prior to the first dose of study medication.
- Randomization stratification factors derived from actual data (not the ones from the randomization system) will be used in all applicable analysis models
 - The stratification factors to be included in the analyses, where appropriate, include the randomization stratification factors and incident dialysis within ≤ 4 months vs. > 4 months of starting dialysis when randomized.
- When the actual treatment received by a subject is different from the randomized treatment assigned, the subject will be analyzed per the randomized treatment for the efficacy parameters; while they will be analyzed per actual treatment that was taken for the safety parameters for US submission.
- Unscheduled visits within an allowable window will be grouped into the closest scheduled visits based on the visit window specified in Appendix 5. For subjects who have more than one measurement at a certain scheduled visit, the last measurements will be used, with the exception of CPK, WBC, liver function tests (i.e., ALT, AST, GGT, ALP, and total bilirubin), in which the maximum measurement will be used.
- By default, US conventional units will be used for laboratory value presentations. A set of lab summary tables in SI units will also be provided based on TLF index.
- Age is calculated as of date that the informed consent form was signed.

age = INTCK('YEAR', Birth date, date of Informed Consent, 'C') where INTCK is a SAS function.

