Change from baseline in SF-36 PF sub-score to the average PF sub-score of weeks 12 to 28 will be analyzed using MMRM model with baseline PF subscore as a covariate, treatment group, visit, the interaction of treatment and visit, and stratification factors as fixed effects. The same strategy as that used in MMRM for Hb will be used to choose variance covariance structure. Data up to visit of Week 52 will be included in the analyses. The estimates for the difference of change from baseline in SF-36 PF for Week 12 to 28 between the two treatment groups will be generated from an estimate statement.

- Vitality Sub-score of SF-36: In subjects with baseline vitality sub-score below 50.
- Physical Functioning Sub-scores of SF-36:
 - In FAS subjects with baseline physical Functioning scores below 40.
 - In all FAS subjects.
- Anemia Subscale (“Additional Concerns”) of Functional Assessment of Cancer Therapy-Anemia (FACT-An) Scores:
 - In FAS subjects with baseline subscale scores below 55 (generally associated with fatigue).
 - In all FAS subjects.
- Total FACT-An Scores:
 - In FAS subjects with baseline FACT-An scores below 135
 - In all FAS subjects.
- EQ-5D-5L Scores: In all FAS subjects.

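### SAP Table 12 puts Days 113-168 in no HRQoL window, so an off-schedule, non-EOT form from a continuing subject drops out of the Weeks 12-28 analyses

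*SAP*

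**What the plan says.** SAP Table 12 defines HRQoL analysis visits as offsets from a target day of 7 x week + 1:

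- Week 12: "Target day -14, Target Day + 27"
- Week 28: "Target Day – 28, Target Day +83"
- Week 52: "Target Day – 84, Target Day + 83"
- EOT row: "Last assessment between Day 2 and EOT visit day, remapped to the closest next scheduled visit for HRQoL collection"

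SAP Section 5.4 states: "Unscheduled visits within an allowable window will be grouped into the closest scheduled visits based on the visit window specified in Appendix 5". If two values share a window, the last one is used (Section 5.4 and the text under Table 13).

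The windows feed the analyses in SAP Section 11.3.7, for example: "Change from baseline in SF-36 PF sub-score to the average PF sub-score of weeks 12 to 28 will be analyzed using MMRM model". SF-36 Vitality is estimated over the same period. SAP Section 4.3 also lists FACT-An and EQ-5D-5L over Weeks 12 to 28.

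For Weeks 4 to 24, Protocol Section 7.1.2.3 schedules one administration: "Week 12: HRQoL questionnaires (SF-36, FACT-An, and EQ-5D-5L"). The other post-baseline administrations are at Weeks 28 and 52 (Section 7.1.2.4) and at EOT/ET (Section 7.1.2.5).

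**The concern.** Analysis windows exist to place assessments that miss their nominal day. A hole between two adjacent windows, inside the interval being averaged, discards on-treatment questionnaires that describe exactly the period of interest.

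The hole also makes inclusion depend on what happens later. A form from these days counts if it turns out to be the subject's last before stopping, through the EOT row. It does not count if the subject stays on treatment and completes later forms. In an open-label trial such a rule is better removed in advance than settled during programming.

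At stake are the precision and clarity of the Weeks 12-28 HRQoL estimates.

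**Working it through.** The SAP gives the windows only as offsets, so there is no stated day range to reproduce. The inputs are the Table 12 and Table 13 offsets and the protocol visit schedule.

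**Step 1. Convert Table 12 to days** (target = 7 x week + 1).

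| Visit | Target | Lower limit | Upper limit |
|---|---|---|---|
| Week 12 | 7 x 12 + 1 = 85 | 85 - 14 = 71 | 85 + 27 = 112 |
| Week 28 | 7 x 28 + 1 = 197 | 197 - 28 = 169 | 197 + 83 = 280 |
| Week 52 | 7 x 52 + 1 = 365 | 365 - 84 = 281 | 365 + 83 = 448 |

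Between Week 12 and Week 28 the unassigned days are 113 to 168: 168 - 113 + 1 = 56 days. Days 2-70 are also unassigned, but they precede the interval being averaged.

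**Step 2. Compare the two boundaries.** The midpoint of Weeks 28 and 52 is (197 + 365)/2 = 281. Week 28 ends on Day 280 and Week 52 starts on Day 281, so that boundary is contiguous at the midpoint. The midpoint of Weeks 12 and 28 is (85 + 197)/2 = 141. The same rule would put the boundary at Day 140/141, but the table has 112/169.

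**Step 3. Compare with the lipid windows.** Table 13 gives lipid Week 12 as "Scheduled Day -14, Scheduled Day +27", the same offsets as HRQoL Week 12, and starts lipid Week 28 at the same -28. Its Week 20 row (target 141, -28/+27) covers 141 - 28 = 113 to 141 + 27 = 168, exactly the HRQoL hole. HRQoL has no Week 20 visit.

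**Step 4. Find which forms are affected.**

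- Scheduled forms at the ±4-day tolerance: Week 12 on Days 81-89, Week 28 on Days 193-201. Both lie inside their windows.
- Clinic visits with target days in the hole: Weeks 16, 18, 20 and 22 (Days 113, 127, 141, 155). Week 16 with tolerance spans Days 109-117, so a make-up form there is kept through Day 112 and dropped from Day 113.
- Week 24: the target, Day 169, is inside the Week 28 window. Only a visit held early, on Days 165-168, falls in the hole.
- EOT/ET forms: remapped, whatever their day.

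**Step 5. Trace one form, Day 130.** It is 130 - 85 = 45 days after the Week 12 target and 197 - 130 = 67 days before the Week 28 target. If it is the last form before stopping, the EOT row sends it to Week 12 (read as closest) or Week 28 (read as next), so it enters the analysis either way. If the subject continues, it has no analysis visit and is not used. By contrast, a form 83 days after the Week 28 target is accepted as Week 28.

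**The case against.** The strongest reply is that almost nothing should land in the hole. No non-EOT questionnaire is scheduled there, and nothing in the protocol provides for making up a missed Week 12 form at a later visit. Protocol Section 7.3 only asks that visits be kept within their window. The one postponement rule (the footnote in Section 7.1.2.4) moves forms to the EOT visit, which the EOT row covers. The unscheduled-visit column of Protocol Appendix 3 is blank for HRQoL. All of this stands, and it makes the expected effect small.

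Second, windows need not be contiguous, and declining to label a Day 140 form as Week 12 is defensible in itself. It fits poorly with the rest of Table 12, however, which accepts Week 28 forms 83 days late and Week 52 forms 84 days early.

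Third, under the last-value rule a wider Week 12 window would let a Day 130 form displace an on-time Day 85 form. That is correct, and the fix has to deal with it.

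Four stronger readings are tempting and not supported:

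- That questionnaires planned for Weeks 16-24 are excluded. None is planned there except EOT/ET forms, which are remapped.
- That half the data are lost, because the hole is 56 of the 113 days from Day 85 to Day 197. That is a share of calendar days, not of forms.
- That accepting Week 28 forms to Day 280 is a separate error. It follows the table's own midpoint convention.
- That the lipid windows were copied without their Week 20 row. The match is exact, but the copying is an inference.

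**Conclusion.** The defect is real and minor. Days 113-168 have no HRQoL window, the table's other boundary shows no such hole, and no reason is given. It affects only off-schedule, non-EOT forms from continuing subjects.

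The documents give no rate for such forms, so their number is unknown. Purely for scale, an assumed 1% of 600 subjects would be 6 forms and an assumed 5% of 1200 would be 60. These figures only multiply out the assumption. The expected consequence is a small loss of precision.

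A reader might infer that a multiplicity-controlled claim is at risk, because Protocol Section 3.2.2 lists SF-36 Physical Functioning and Vitality over Weeks 12-28 as secondary endpoints, and non-inferiority with a 2-point margin is kept in SAP Section 11.3.7. The documents do not support that. The SAP leaves both out of its secondary endpoints (Section 4.2) and out of the fixed sequence (Table 6), places them among additional evaluations (Section 4.3), and describes the Section 11.3.7 endpoints as exploratory. The primary test is not touched.

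**What to change.** Apply Table 12's own midpoint rule:

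- Week 12: Target Day -14 to Target Day +55 (85 + 55 = 140), Days 71-140.
- Week 28: Target Day -56 to Target Day +83 (197 - 56 = 141), Days 141-280.
- Week 52: unchanged.

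For HRQoL, when two forms fall in one window, use the one closest to the target day, with a stated rule for ties. Write this exception to the last-value rule in both Section 5.4 and Section 16.5.1. It keeps a late ad hoc form from replacing an on-time Week 12 form, and does the same in the long Week 28 window.

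State whether *closest next* in the EOT row means closest or next, and settle it together with the selection rule. For an ET form on Day 120, *next* fills Week 28, whereas *closest* makes it compete with the Week 12 form (35 days from target against 77).

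The cost is two offsets and two sentences in the SAP, with no new data. The downside is that some forms up to 56 days (8 weeks) from target would be labelled Week 12 or Week 28. All the added days, 113-168, lie inside the Weeks 12-28 interval being averaged.
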